**Missing data:**

We will not use a multiple imputation method because we assume that the missingness of the outcome data is not random. Instead, it likely depends on the difference in effectiveness between the LTCR and HTCR interventions and is therefore related to the true outcome values. Consequently, we will conduct post hoc sensitivity analyses for the primary endpoint using worst-case and best-case scenarios to assess the robustness of our findings. For participants who dropped out, VISA-A scores from the last observation will be carried forward. Additionally, in the worst-case scenario (favoring the control group), missing values will be replaced by the group mean + 2 SD in the HTCR group, and the group mean - 2 SD in the LTCR group at both time point. In the best-case scenario (favoring the interventional group), this approach will be reversed.

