**Sample size:**

A sample size calculation was conducted a priori based on the primary outcome measure, the VISA-A score. To detect a clinically significant mean difference of 10 points in the VISA-A score, with 90% power and a standard deviation of 8.4, and with an alpha level of 0.05, a total of 40 participants would be required. This calculation also accounts for a 20% dropout rate.

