**Primary endpoint and measure:**

Primary endpoint is mean difference in score on the Victorian Institute of Sports Assessment-Achilles (VISA-A) questionnaire at 12 and 24 weeks between LTCR and HCTR. This validated, reliable, self-administered patient-reported outcome evaluates Achilles tendon pain, function, and ability to play sports. The maximum score is 100, with a lower score indicating greater clinical severity.

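### The best-case and worst-case fill for missing VISA-A scores has no cap and can exceed the scale maximum of 100 (minor)

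*SAP*

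**What the plan says.** Section 6 of the SAP (Missing data) declines multiple imputation because missingness is assumed not to be random. It plans sensitivity analyses of the primary endpoint "using worst-case and best-case scenarios to assess the robustness of our findings". In the worst case, "missing values will be replaced by the group mean + 2 SD in the HTCR group", and the LTCR group receives "the group mean - 2 SD in the LTCR group at both time point". For the other scenario, "In the best-case scenario (favoring the interventional group), this approach will be reversed". No limit on the filled value is stated there or anywhere else in the SAP.

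Section 6 (Primary endpoint and measure) describes VISA-A: "The maximum score is 100, with a lower score indicating greater clinical severity". The only SD in the SAP is in Section 3 (Sample size), which plans for a "mean difference of 10 points in the VISA-A score, with 90% power and a standard deviation of 8.4". No expected follow-up mean is given for either arm.

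**The concern.** The SAP fixes the imputation formula itself, so a programmer who follows it literally has no reason to stop at 100. If a group does well, its missing patients can be given scores that no patient could have. The best-case and worst-case pair is the SAP's named check on whether dropout could explain the primary result, and that check should use attainable scores. Part of the reported distance between the two scenarios could otherwise come from values off the scale.

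The problem is practically confined to the upper end. At SD 8.4 the minus 2 SD fill falls below 0 only for a group mean under 2 × 8.4 = 16.8. Even at an assumed SD of 20 the mean would have to be under 40.

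**Working it through.** **Inputs from the SAP.** VISA-A maximum 100; fill = group mean ± 2 SD; SD 8.4; target difference 10 points; dropout 20%; total 40, allocated 1:1, so 20 per arm.

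**Assumptions.** 4 of 20 per arm are filled (the planned 20%). Follow-up means, and SDs other than 8.4, are not in the SAP and are shown as a range.

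**The plan's own figure.** The SAP states that "with an alpha level of 0.05, a total of 40 participants would be required". A two-sided two-sample t-test for 10 points, SD 8.4 and 90% power needs 15.85, so 16 per arm; 16 / 0.8 = 20 per arm, or 40 in total. This reproduces. It also gives the split of 16 observed and 4 filled per arm used below.

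**When the fill leaves the scale.** Mean + 2 SD > 100 when mean > 100 − 2 SD:

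| SD | Threshold group mean |
|---|---|
| 8.4 (SAP) | 83.2 |
| 12 (assumed) | 76 |
| 15 (assumed) | 70 |

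**Effect on the difference, LTCR minus HTCR.** With a fraction 0.2 filled and equal SDs, each arm mean moves by 0.2 × 2 SD. So the uncapped best case = true difference + 0.8 SD, and the uncapped worst case = true difference − 0.8 SD. An arm filled upward is overstated by 0.2 × max(0, mean + 2 SD − 100).

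Worked example, SD 8.4, HTCR 75, LTCR 85:
- LTCR fill = 85 + 16.8 = 101.8.
- Best case, uncapped: 10 + 6.72 = 16.72.
- Best case, capped: LTCR 0.8 × 85 + 0.2 × 100 = 88; HTCR 75 − 3.36 = 71.64; difference 16.36.
- Overstatement: 0.2 × 1.8 = 0.36.
- Worst case: HTCR fill = 91.8, on the scale, so 10 − 6.72 = 3.28 with or without a cap.

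| SD | HTCR / LTCR mean | Best case, uncapped → capped | Worst case, uncapped → capped |
|---|---|---|---|
| 8.4 | 75 / 85 | 16.72 → 16.36 | 3.28, unchanged |
| 8.4 | 80 / 90 | 16.72 → 15.36 | 3.28, unchanged |
| 12 | 75 / 85 | 19.60 → 17.80 | 0.40, unchanged |
| 15 | 75 / 85 | 22.0 → 19.0 | −2.0 → −1.0 |
| 15 | 80 / 80 | 12.0 → 10.0 | −12.0 → −10.0 |
| 15 | 85 / 75 | 2.0 → 1.0 | −22.0 → −19.0 |

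The last two rows show the mirror image. With equal means the distortion is symmetric, and with HTCR ahead the larger distortion is in the worst case.

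**Allowing for the ceiling in the observed data.** The formula takes the mean and SD as given, but scores held at 100 lower both. In a simulation (normal scores limited to 100, 16 observed and 4 filled per arm, means 75 and 85 before the limit):
- SD 8.4: the LTCR fill exceeds 100 in about 62% of trials. Best case 16.4 uncapped, about 16.1 capped; worst case 3.4 either way.
- SD 15: the LTCR fill exceeds 100 in about 98% of trials. Best case 19.9 uncapped, 18.0 capped; worst case −1.7 and −0.9.

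So at SD 15 the overstatement is nearer 2 points than 3 in the best case, and 0.8 rather than 1 in the worst case.

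**The case against.** **Direction.** A reader might infer that the missing cap favours LTCR. The SAP does not support that. Each arm gets the upward fill once and the downward fill once. The LTCR overshoot is larger only if LTCR has the higher mean (or a larger SD, or more missing scores). That is the trial's hypothesis, not a property of the rule.

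**Consequence for a superiority claim.** A reader might also infer that a positive result would be flattered. The scenario that tests such a result is the worst case. Overshoot there raises HTCR and so makes the test harsher for LTCR. What is flattered is the best case, which should carry no efficacy claim. This objection stands.

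**Bounds.** Mean ± 2 SD was never a strict limit on possible outcomes, and a fill above 100 is looser still rather than too tight. So the rule does not lose a guarantee that it once had. What remains is that part of the scenario is built on unattainable values.

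**Plausibility.** Entry requires VISA-A below 80, but that is an upper limit, and stratification at 50 suggests that many entrants may start well below it. At SD 8.4 and group means of 83.2 or less, no filled score exceeds 100. The problem is therefore conditional.

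**Share filled.** The same section also carries the last observation forward for dropouts before adding the ± 2 SD scenarios, and does not make clear how the two combine. If carried-forward values stand in the scenarios, fewer scores receive the ± 2 SD fill and the shifts shrink in proportion.

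None of this supplies the missing limit.

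**Conclusion.** The point holds as a minor defect in a stated rule. Followed literally, the fill gives impossible scores once a group mean exceeds 83.2 at the plan's SD, or a lower threshold if the SD is larger.

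On the plan's SD, with 20% filled, the best-case difference is overstated by about 0.4 to 1.4 points for an assumed LTCR mean of 85 to 90, against a 10-point target. The worst case does not move while the HTCR mean is 83.2 or less. Shifts of about 1 to 3 points arise only at an assumed SD near 15, and the upper end of that range ignores the ceiling's effect on the observed data.

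The sample size and the main mixed-model analysis are untouched. The missing cap is certain; the size of its effect rests on follow-up means, and partly on SDs, that the SAP does not give.

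**What to change.** Add one sentence to Section 6, Missing data: *Imputed VISA-A scores are limited to the scale: min(100, group mean + 2 SD) and max(0, group mean − 2 SD), in both scenarios and at both time points.*

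The cost is that sentence and one line of code. The scenarios become slightly less extreme when the ceiling is reached and do not change otherwise.

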**Intercurrent events:**

In line with the 'intention-to-treat' principle, we will disregard intercurrent events, such as treatment discontinuation, during analysis.

**Statistical software:**

Data will be analysed by using IBM SPSS version 28 or more recent.

